### **5.7.3 Pregnancy**

If a subject inadvertently becomes pregnant while on treatment with preladenant and/or pembrolizumab, the subject will be immediately discontinued from study treatment. The site will contact the subject at least monthly and document the subject's status until the pregnancy has been completed or terminated. The outcome of the pregnancy will be reported to the Sponsor without delay and within 24 hours if the outcome is a serious adverse reaction (e.g., death, abortion, congenital anomaly, or other disabling or life-threatening complication to the mother or newborn). The study Investigator will make every effort to obtain permission to follow the outcome of the pregnancy and report the condition of the fetus or newborn to the Sponsor. If a male subject impregnates his female partner, the study personnel at the site must be informed immediately and the pregnancy must be reported to the Sponsor and followed as described in Section 7.2.

### **5.7.4 Use in Nursing Women**

It is unknown whether preladenant and/or pembrolizumab are excreted in human milk. Since many drugs are excreted in human milk, and because of the potential for serious adverse reactions in the nursing infant, subjects who are breast-feeding are not eligible for enrollment.

## **5.8 Subject Withdrawal/Discontinuation Criteria**

### **5.8.1 Discontinuation of Treatment**

Discontinuation of treatment does not represent withdrawal from the trial.

As certain data on clinical events beyond treatment discontinuation may be important to the study, they must be collected through the subject's last scheduled follow-up, even if the subject has discontinued treatment. Therefore, all subjects who discontinue trial treatment prior to completion of the treatment period will still continue to participate in the trial as specified in Section 6.0 - Trial Flow Chart and Section 7.1.5. – Visit Requirements .

Subjects may discontinue treatment at any time for any reason or be dropped from treatment at the discretion of the investigator should any untoward effect occur. In addition, a subject may be discontinued from treatment by the investigator or the Sponsor if treatment is inappropriate, the trial plan is violated, or for administrative and/or other safety reasons. Specific details regarding procedures to be performed at treatment discontinuation are provided in Section 7.1.4 – Other Procedures.

A subject must be discontinued from treatment but continue to be monitored in the trial for any of the following reasons:

- The subject or subject's legally acceptable representative requests to discontinue treatment.
- Non-compliance with trial treatment or procedure requirements.
- A confirmed positive serum pregnancy test.
- Confirmed radiographic disease progression outlined in Section 7.1.5 (exception if the Sponsor approves treatment continuation).
  - A subject with confirmed radiologic progression may continue to receive study treatment, after consultation with the Sponsor, if the investigator deems the subject is receiving clinical benefit or value from treatment.
- Unacceptable adverse experiences as described in Section 7.2.
- Intercurrent illness other than another malignancy as noted above that prevents further administration of treatment.
- Investigator's decision to discontinue treatment.
- Recurrent Grade 2 pneumonitis.
- Progression or recurrence of any malignancy, or any occurrence of another malignancy that requires active treatment.
- Completion of 35 treatments with preladenant and/or pembrolizumab.

Note: 35 cycles (approximately 2 years) are calculated from the first dose

- Administrative reasons.

For subjects who are discontinued from treatment but continue to be monitored in the trial, all visits and procedures, as outlined in the trial flowchart, should be completed.

Subjects who discontinue preladenant in the monotherapy arm due to disease progression may at the Investigator's discretion and after consultation with the Sponsor, cross-over to combination treatment. The subject will receive the dose of preladenant that has been determined to be safe in the combination arm (e.g., 1 dose level below the dose being tested) at the time of treatment cross-over. The preladenant dose will not exceed the dose the subject received in the monotherapy arm. The first dose of combination treatment will not occur until the 21-day Cycle 1 of preladenant monotherapy treatment finishes.

Specific details regarding procedures to be performed are provided in the Arm 2 Study Flowchart in Section 6.0.

For subjects who are discontinued from treatment but continue to be monitored in the trial, all visits and procedures, as outlined in the trial flowchart, should be completed.

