Duration of Participation	
Each subject will participate in the trial for up to 28 months from the time the subject signs the informed consent form (ICF) through the final protocol-specified contact.
 
After a screening phase of up to 28 days, each subject will be receiving assigned treatment for up to 24 months. After treatment discontinuation, subjects will be monitored for adverse events (AEs) and serious adverse events (SAEs) for 90 days. Subjects who initiate new anticancer therapy less than 30 days after study treatment discontinuation will be monitored for AEs/SAEs for 30 days. Subjects who initiate new anticancer therapy between 30 days and 90 days after study treatment discontinuation will be monitored for AEs/SAEs until the day new anticancer therapy is initiated. Subjects will be treated until progressive disease, unacceptable toxicity, intercurrent illness that prevents further administration of treatment, investigator's decision to withdraw treatment, subject withdrawal of consent, pregnancy of the subject, noncompliance with trial treatment or procedure requirements, subject completes treatment, or administrative reasons requiring cessation of treatment, at which point they will be discontinued from the study. Upon disease progression, subjects in the monotherapy arm will be able to cross-over to the combination regimen.

Randomization Ratio	N/A

A list of abbreviations used in this document can be found in Section 12.6.

Preladenant will be used throughout the protocol to refer to MK-3814 as supplied by the Sponsor.

Pembrolizumab will be used throughout the protocol to refer to KEYTRUDA® or MK-3475 as supplied by the Sponsor.

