Immune-related RECIST (irRECIST) is RECIST 1.1 adapted to account for the unique tumor response seen with immuno-therapeutics as described by Nishino, et al. [20]. Immunotherapeutic agents may produce antitumor effects by potentiating endogenous cancer-specific immune responses. The response patterns seen with such an approach may extend beyond the typical time course of responses seen with cytotoxic agents, and

participants can manifest a clinical response after an initial increase in tumor burden or even the appearance of new lesions.

Based on an analysis of patients with melanoma enrolled in Keynote-001, 7% of evaluable patients experienced delayed or early tumor pseudoprogression. Of note, patients who had progressive disease by RECIST 1.1 but not by immune related Response Criteria had longer OS than patients with progressive disease by both criteria. Additionally, the data suggest that RECIST 1.1 may underestimate the benefit of pembrolizumab in approximately 15% of patients. These findings support the need to apply a modification to RECIST 1.1 that takes into account the unique patterns of atypical response in immunotherapy and enable treatment beyond initial radiographic progression.

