#### **7.1.2.6.2 Tumor Imaging During Trial**

The first on-trial imaging assessment should be performed at 9 weeks (63 days  $\pm$ 7 days) from the date of randomization. Subsequent tumor imaging should be repeated every 9 weeks or more frequently if clinically indicated. Imaging timing should follow calendar days and should not be adjusted for delays in cycle starts. Imaging should continue to be performed until disease progression, the start of new anti-cancer treatment, withdrawal of consent, or death, whichever occurs first.

Per RECIST 1.1, partial and complete response should be confirmed by a repeat tumor imaging assessment not less than 4 weeks from the date the response was first documented. The tumor imaging to confirm a response may be performed, at the earliest 4 weeks after the first indication of a response, or at the next scheduled scan (i.e., 9 weeks later), whichever is clinically indicated. Subjects will then return to regular scheduled imaging every 9 weeks, starting with the next scheduled imaging time point. Subjects who obtain a confirmation scan do not need to undergo the next scheduled tumor imaging if it is <4 weeks later; tumor imaging may resume at the subsequent scheduled imaging time point.

Per irRECIST (Section 7.1.2.6.5), disease progression should be confirmed by the site at least 4 weeks after site-assessed first radiologic evidence of PD in clinically stable subjects. Subjects who have unconfirmed disease progression may continue on treatment at the discretion of the site Investigator until progression is confirmed by the site provided they have met the conditions detailed in Section 7.1.2.6.5. Subjects who obtain a confirmation scan do not need to undergo the next scheduled tumor imaging if it is <4 weeks later; tumor imaging may resume at the subsequent scheduled imaging time point if clinically stable. Subjects who have confirmed disease progression as assessed by the site, will discontinue trial treatment. Exceptions are detailed in Section 7.1.2.6.5.

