#### **7.1.2.6.5 irRECIST Assessment of Disease**

irRECIST is RECIST 1.1 adapted as described below to account for the unique tumor response seen with immunotherapeutic drugs. irRECIST will be used by the site Investigator/local radiology reviewers to assess tumor response and progression, and make treatment decisions. This data will be collected in the clinical database.

When feasible, subjects should not be discontinued until progression is confirmed by the local site Investigator/radiology assessment. This allowance to continue treatment despite initial radiologic PD takes into account the observation that some subjects can have a transient tumor flare in the first few months after the start of immunotherapy, and then experience subsequent disease response. Subjects that are deemed clinically unstable are not required to have repeat tumor imaging for confirmation of PD. Tumor flare includes any of the following scenarios:

- Worsening of existing target lesion(s)
- Worsening of existing nontarget lesion(s)
- Development of new lesion(s)

In subjects who have shown initial evidence of radiological PD by RECIST 1.1, it is at the discretion of the Investigator whether to continue a subject on trial medication until repeat imaging is obtained (using irRECIST for subject management (see [Table 12](#)). This clinical judgment decision by the site Investigator should be based on the subject's overall clinical condition, including performance status, clinical symptoms, and laboratory data. Subjects may receive trial medication and the tumor assessment should be repeated  $\geq 4$  weeks later in order to confirm PD by irRECIST per site assessment. Clinical stability is defined as the following:

- Absence of symptoms and signs indicating clinically significant progression of disease, including worsening of laboratory values
- No decline in ECOG performance status
- Absence of rapid progression of disease
- Absence of progressive tumor at critical anatomical sites (e.g., cord compression) requiring urgent alternative medical intervention

Any subject deemed clinically unstable should be discontinued from trial treatment at site-assessed first radiologic evidence of PD and is not required to have repeat imaging for PD confirmation.

In determining whether or not the tumor burden has increased or decreased per irRECIST, the local site Investigator should consider all target and non-target lesions, as well as any incremental new lesion(s).

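### Section 5.8.1 contradicts itself on stopping treatment for progression: one mandatory bullet requires confirmation, a later one does not and conflicts with the irRECIST provisions

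*Combined protocol and SAP*

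**What the plan says.** The list in Section 5.8.1 is mandatory. Its lead-in is "A subject must be discontinued from treatment but continue to be monitored in the trial for any of the following reasons". Two of its bullets concern progression:

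- The first is "Confirmed radiographic disease progression outlined in Section 7.1.5 (exception if the Sponsor approves treatment continuation"), with a sub-bullet on continuing after confirmed progression where the investigator sees benefit and the sponsor has been consulted.
- The second, lower in the same list, is "Progression or recurrence of any malignancy, or any occurrence of another malignancy that requires active treatment".

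The imaging sections address a first PD directly. Section 7.1.2.6.5 says "When feasible, subjects should not be discontinued until progression is confirmed by the local site Investigator/radiology assessment", and adds that, when a scan first meets the RECIST 1.1 definition of PD, "it is at the discretion of the Investigator whether to continue a subject on trial medication until repeat imaging is obtained". Section 7.1.2.6.2 says "Subjects who have unconfirmed disease progression may continue on treatment at the discretion of the site Investigator until progression is confirmed by the site", subject to the conditions in 7.1.2.6.5. Sections 2.1 and 4.2.3.2 and Table 12 say the same in substance. Section 4.2.3.2 puts the repeat assessment at least 4 weeks later, and Table 12 limits continuation to clinically stable subjects.

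The general statements on treatment duration carry no confirmation condition. Section 1.0 says "Subjects will be treated until progressive disease, unacceptable toxicity, intercurrent illness that prevents further administration of treatment", and Section 5.2.1.4 is worded to the same effect.

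**The concern.** A site that keeps a stable subject on treatment after a first PD follows Section 7.1.2.6.5 but breaches the literal wording of the later bullet in 5.8.1. A site that obeys the later bullet stops the subject regardless of clinical stability. The confirmation condition and the sponsor exception in the other bullet then have no effect. Protocol compliance at first PD cannot be judged consistently while both stand.

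The statistical interest lies in exploratory objective 3, ORR and PFS by irRECIST. Section 4.2.3.2 adopts irRECIST so that treatment can go on beyond an initial radiographic progression. If a subject is stopped at first PD and no later scan is taken, the PD can be neither confirmed nor refuted, and a later response on treatment cannot be observed. Treatment duration (summarised in cycles under Section 8.12) and the time at which an Arm 1 subject becomes a candidate for cross-over also depend on which bullet a site applies.

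**Working it through.** The plan gives no figure of its own on this point, so the main check is a comparison of text.

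**The passages side by side**

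| Place | Confirmation needed before stopping? | Exception or discretion? |
|---|---|---|
| 5.8.1, confirmed-progression bullet | Yes | Yes, with sponsor approval |
| 5.8.1, later malignancy bullet | No | None |
| 1.0 and 5.2.1.4 | Not stated | None stated |
| 2.1, 4.2.3.2, 7.1.2.6.2 | Treatment may continue until the repeat scan | Investigator discretion |
| 7.1.2.6.5 and Table 12 | Sites asked to wait when feasible; clinically unstable subjects stop | Investigator discretion for stable subjects; sponsor exception after confirmation |

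1. *Does the later bullet reach the study tumour?* It first refers to any malignancy and then separately to another malignancy. If the first part meant only other cancers, the separate mention would be unnecessary. On plain wording it includes the cancer under study.
2. *Is the bullet compatible with the other one?* No. Every confirmed progression is also a progression, so the later bullet already covers it, without the exception. The later bullet also covers unconfirmed progression, which the first bullet leaves out.
3. *Does the cross-reference resolve it?* No. The confirmed-progression bullet points to Section 7.1.5, Visit Requirements. The criteria for confirmed and not-confirmed PD are in 7.1.2.6.5.
4. *Would later scans be taken anyway?* Only in part. Section 7.1.2.6.3 makes the discontinuation scan the last one required when the stop was for documented progression. Section 7.1.5.3.3 continues imaging when the stop was for something other than verified PD. Neither says on which side a single unconfirmed PD falls.
5. *Which endpoints are exposed?* The DLT window is Days 1 to 21 and the first on-trial scan is at 63 ± 7 days, so the primary endpoint is settled before the issue can arise. RECIST 1.1 takes the first PD as progression, so the secondary ORR is largely unaffected. irRECIST ORR and PFS are exposed.

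**Scale, for illustration only**

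Inputs: n = 30 per Part 2 cohort (Section 5.2.1.3). Pseudoprogression rate r = 0.07, from Section 4.2.3.2: "7% of evaluable patients experienced delayed or early tumor pseudoprogression". That rate is from melanoma, and its transfer to the Part 2 tumours is an assumption. The share s of subjects stopped at first PD is not in the documents, so a range is shown.

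Expected subjects = n × r × s. Chance of at least one = 1 − (1 − r × s)^30.

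| s | Expected subjects | Share of cohort | Chance of at least one |
|---|---|---|---|
| 25% | 30 × 0.07 × 0.25 = 0.53 | 1.75 points | 41% |
| 50% | 30 × 0.07 × 0.50 = 1.05 | 3.5 points | 66% |
| 100% | 30 × 0.07 × 1.00 = 2.1 | 7.0 points | 89% |

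The share of the cohort is an upper bound on the loss in irRECIST ORR, because not every subject with pseudoprogression goes on to respond. The count is proportional to r. With everyone stopped, an assumed r of 3% gives 30 × 0.03 = 0.9 subjects and an assumed r of 15% gives 30 × 0.15 = 4.5.

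**The case against.** The best defence is that the operative rule is clear from the rest of the protocol. Five places allow treatment past a first PD, and the study cancer has its own bullet with its own exception. That bullet would be pointless if the later one covered the same ground. Pairing the later bullet with another malignancy needing treatment suggests it was meant for second cancers. This is plausible as intent and may be how many sites would read it. The wording does not say so, however, and the list is headed by a mandatory instruction.

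Second, investigators already have discretion at first PD, so sites may differ whatever 5.8.1 says. That stands, and correcting the bullet would not remove all variation. But the discretion in 7.1.2.6.5 is tied to clinical condition with listed stability criteria, whereas the literal bullet applies regardless of condition.

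Third, later information is not necessarily lost. Table 12 allows repeat imaging, and a restart of treatment, for subjects stopped as clinically unstable, and Section 7.1.5.3.3 may keep scans going. This reduces the loss but does not exclude it, given Section 7.1.2.6.3.

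Fourth, cross-over already needs investigator judgement and sponsor consultation, and Sections 8.5.1 and 8.5.2 present cross-over data separately. The effect there is confined to timing.

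**Conclusion.** The point holds as an internal inconsistency, wrong as written, of low to moderate severity. The two bullets in 5.8.1 cannot both be followed, and the later one conflicts with the provisions for treatment past first PD. The exposure is limited to exploratory irRECIST ORR and PFS, treatment duration and cross-over timing. On the 7% rate it is about 0.5 to 2.1 subjects per 30-subject cohort, and at most 7 points of irRECIST ORR if every subject were stopped at first PD. This rests on the transfer of a melanoma rate and on an unknown share stopped.

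A reader might infer two stronger things. One is that some sites will stop at first PD and that the irRECIST endpoints will be uneven for that reason. The documents show only that this could happen: nothing indicates that sites would follow the bullet over the dedicated imaging section, and discretion already permits variation. The other is a loss of up to 15 points, taken from the statement in Section 4.2.3.2 that RECIST 1.1 may understate pembrolizumab's benefit in about 15% of patients. That figure describes understated benefit. It does not count subjects whose irRECIST outcome would be missed, so it gives no basis for a loss of that size.

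**What to change.** Reconcile Sections 1.0, 5.2.1.4, 5.8.1, 7.1.2.6.2, 7.1.2.6.3, 7.1.2.6.5 and 7.1.5.3.3 so that a single rule states what happens to treatment at a first, unconfirmed PD of the cancer under study. State which malignancies the later bullet in 5.8.1 covers. Point the confirmed-progression bullet to 7.1.2.6.5 instead of 7.1.5. Say whether an unconfirmed PD counts as documented or verified for the purpose of continued imaging. Which clinical rule applies is for the sponsor and investigators to decide.

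Separately, the supplemental SAP should say how irRECIST ORR and PFS treat a first PD that has no confirmation scan, since investigator discretion can produce such cases even after the wording is corrected.

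The cost is a clarification letter or amendment text, plus a short paragraph in the supplemental SAP. The reconciliation itself needs no new procedures or subjects.

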### **5.8.2 Withdrawal from the Trial**

A subject must be withdrawn from the trial if the subject or subject's legally acceptable representative withdraws consent from the trial.

If a subject withdraws from the trial, they will no longer receive treatment or be followed at scheduled protocol visits.

Specific details regarding procedures to be performed at the time of withdrawal from the trial including the procedures to be performed should a subject repeatedly fail to return for scheduled visits and/or if the study site is unable to contact the subject, as well as specific details regarding withdrawal from Future Biomedical Research are outlined in Section 7.1.4 – Other Procedures.

### **5.9 Subject Replacement Strategy**

In order to adequately evaluate the safety of the doses administered in this study, all subjects enrolled must meet the criteria for evaluability for Cycle 1. Subjects are considered non-evaluable and will be replaced if:

- They are allocated but not treated
- They discontinue from the trial prior to completing all the safety evaluations for reasons other than treatment-related adverse events
- They receive less than 90% of the total pembrolizumab infusion in Cycle 1 (e.g., if the infusion had to be discontinued due to an infusion reaction) and did not experience a DLT

Subjects who are not evaluable will be replaced unless accrual to the cohort has stopped. Non-evaluable subjects will not be counted toward the total number of subjects in the cohort for DLT evaluation.

If a subject experiences a DLT in Cycle 1, trial treatment may be discontinued following discussion between the sponsor and Investigator. However, if the subject is deriving clinical benefit from the trial treatment, the subject may be allowed to continue after discussion between the sponsor and the Investigator.

A subject who discontinues from trial treatment or withdraws from the trial during or after Cycle 2 (See Section 5.2.2.1 for subject replacement during Cycle 1) will not be replaced.

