**SUMMARY OF CHANGES**

**PRIMARY REASON(S) FOR THIS AMENDMENT:**

Section Number (s)	Section Title(s)	Description of Change (s)	Rationale
1.0 2.1 6.0 7.1.5.3.2 7.2	Trial Summary Trial Design Flow chart Safety Follow-up Visit Assessing and Recording Adverse Events	The protocol collection period for AEs was revised to 90 days after treatment discontinuation, 30 days if the subject initiates new anticancer therapy less than 30 days after study treatment discontinuation, or the day new anticancer therapy is initiated if between 30 days and 90 days after study treatment discontinuation.	This change was made at the request of the FDA to allow late toxicities that can be observed with immunomodulatory agents to be collected.
2.1 2.2 4.2.2 5.2 Trial Treatment(s)	Trial Design Trial Diagram Rationale for Dose Selection/Regimen	The starting dose has been changed from 10 mg BID to 25 mg BID. A 10 mg BID (DL-1) dose is added as an alternative dose should 25 mg BID prove to be intolerable	This change was made at the request of the FDA to ensure the dose escalation from DL1 to DL2 does not exceed 2 fold.
5.1.2	Subject Inclusion Criteria	Subjects to be enrolled to the study are defined as refractory to or intolerant of existing therapy(ies) known to provide clinical benefit for their condition.	This change was made at the request of the FDA to ensure patients to be enrolled in this trial are those who have exhausted all current approved therapeutic options.
5.1.3	Subject Exclusion Criteria	Examples of A2a receptor antagonists CPI-444, HTL1071, PBF-509 are added to exclusion criteria # 3.	This change was made at the request of the FDA to clarify A2a receptor antagonists that preclude trial inclusion.

Section Number (s)	Section Title(s)	Description of Change (s)	Rationale
5.2.2.1	Replacement of Subjects in DLT period	The protocol was clarified to better describe the situation when patients are experiencing DLT but allowed to remain in the trial. Language is added to define “the subject is deriving clinical benefit upon resolution of the DLT to a $\leq$ Grade 1 adverse event and after discussion with the sponsor.”	This change was made at the request of the FDA as an extra safety precaution.
5.2.3	Guideline for Dose Modification and Treatment Discontinuation”	The protocol was clarified the section is applicable to both part 1 and part 2.	This change was made at the request of the FDA for clarification.

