### **5.2.2 Definition of Dose-Limiting Toxicities**

All toxicities will be graded using NCI CTCAE Version 4.0 based on Investigator assessment (Appendix 12.5).

The DLT window of observation will be during Cycle 1 (Day 1 to Day 21).

The occurrence of any of the following toxicities during Cycle 1 will be considered a DLT, if assessed by the Investigator to be possibly, probably or definitely related to study drug administration:

- 1) Grade 4 non-hematologic toxicity (not laboratory).
- 2) Grade 4 hematologic toxicity lasting  $\geq 7$  days, except thrombocytopenia
  - a) Grade 4 thrombocytopenia of any duration
  - b) Grade 3 thrombocytopenia associated with bleeding
- 3) Grade 3 non-hematologic toxicity (not laboratory) lasting  $>3$  days despite optimal supportive care.

- 4) Any Grade 3 or Grade 4 non-hematologic laboratory value if:
  - Medical intervention is required to treat the subject, or
  - The abnormality leads to hospitalization, or
  - The abnormality persists for >72 hours.
  - Exceptions:
    - Clinically non-significant, treatable, or reversible laboratory abnormalities including uric acid, etc.
- 5) Any of the following liver test abnormalities are observed (Hy's Law)
  - ALT or AST > 3X ULN **with** TBL > 2X ULN with no elevation in alkaline phosphatase (AP < 2X ULN)
  - No other reasons can be found to explain the combination of increased AT and TBL, such as viral hepatitis, A,B or C, preexisting or acute liver diseases, or another drug capable of causing the observed injury
- 6) Febrile neutropenia Grade 3 or Grade 4:
  - Grade 3 is defined as ANC <1000/mm^3 with a single temperature of >38.3 degrees C (101 degrees F) or a sustained temperature of ≥38 degrees C (100.4 degrees F) for more than one hour
  - Grade 4 is defined as ANC <1000/mm^3 with a single temperature of >38.3 degrees C (101 degrees F) or a sustained temperature of ≥38 degrees C (100.4 degrees F) for more than one hour, with life-threatening consequences and urgent intervention indicated.
- 7) Prolonged delay (>2 weeks) in initiating cycle 2 due to treatment-related toxicity.
- 8) Any treatment-related toxicity which causes the subject to discontinue treatment during Cycle 1.
- 9) Missing >25% of Preladenant doses as a result of drug-related AE(s) during the first cycle.
- 10) Grade 5 toxicity.

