### **5.2.2.1 Replacement of Subjects in DLT Period**

In order to fully evaluate the safety of the combination therapy in this study, all subjects enrolled must meet the criteria for evaluability for Cycle 1. Subjects are considered non-evaluable and will be replaced if:

- They are enrolled but not treated,
- They discontinue from the trial prior to completing all safety evaluations due to reasons other than drug-related AEs,
- They received <90% of the total pembrolizumab infusion in Cycle 1 (e.g., because the infusion had to be discontinued due to an infusion reaction) and did not experience a drug-related event,
- They received  $\leq 75\%$  of preladenant doses intended for the trial during Cycle 1 and did not experience a drug-related AE,
- They must take a prohibited concomitant medication during Cycle 1, unless this medication is used to treat a study drug-related AE,
- They must undergo medical / surgical procedures or have logistical issues not related to study therapy (e.g., elective surgery, unrelated medical events) during Cycle 1.

Non-evaluable subjects will not be counted toward the cohort total for DLT evaluation.

Subjects who experience a DLT in Cycle 1 should be discontinued from treatment. However, if in the opinion of the Investigator, the subject is deriving clinical benefit from the study treatment, the subject may be allowed to continue on the study upon resolution of the DLT to a  $\leq$  Grade 1 adverse event and after discussion with the sponsor.

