
 
Any Grade 3 or 4 non-hematological toxicity (not including laboratory, unless clinically significant medical intervention is required to treat the subject, or the abnormality leads to hospitalization, or the abnormality persists for >1 week)
 
	Yes	Treatment may be restarted when AE resolves back to baseline or to Grade 1.	Decrease dose by one dose level.	If AE persists for 12 weeks without resolution following reduction in dose. Permanent discontinuation should be considered for any severe or life-threatening event

In case toxicity does not resolve to Grade 0-1 within 12 weeks after last treatment, preladenant should be discontinued after consultation with the Sponsor.

With Investigator and Sponsor agreement, subjects with a laboratory adverse event still at Grade 2 after 12 weeks may continue treatment in the trial only if asymptomatic and controlled.

After any Grade 4 drug-related adverse event, subjects should not restart study treatment without consultation with the Sponsor. (Toxicity must have resolved to 0-1 or baseline prior to restarting).

Dose reductions are not permitted during Cycle 1.

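### Section 5.9 lets a benefiting subject continue after a Cycle 1 DLT without the resolution to Grade 1 or lower that Section 5.2.2.1 requires

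*Combined protocol and SAP*

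**What the plan says.** Section 5.2.2.1 (Replacement of Subjects in DLT Period) sets the default: "Subjects who experience a DLT in Cycle 1 should be discontinued from treatment". Its exception is for a subject who, in the investigator's opinion, is benefiting. That subject "may be allowed to continue on the study upon resolution of the DLT to a" Grade 1 or lower event, and after discussion with the sponsor.

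Section 5.9 (Subject Replacement Strategy) covers the same event in these terms: "If a subject experiences a DLT in Cycle 1, trial treatment may be discontinued following discussion between the sponsor and Investigator". For a subject deriving clinical benefit it adds that "the subject may be allowed to continue after discussion between the sponsor and the Investigator". It gives no resolution grade. Its only link to the other section reads "See Section 5.2.2.1 for subject replacement during Cycle 1", which concerns replacement and not continuation.

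The Summary of Changes lists 5.2.2.1 as revised on this point, with language on when "the subject is deriving clinical benefit upon resolution of the DLT to a" Grade 1 or lower event. The reason given is an FDA request for extra safety. Section 5.9 is not listed as changed.

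**The concern.** Both sections are current text, so this is not a difference between an amendment log and the protocol. They differ on the default action and on the conditions for continuing. A site that opens 5.9 finds that stopping treatment is optional and that benefit plus a conversation with the sponsor is enough to continue. A site that opens 5.2.2.1 finds that stopping is expected and that the toxicity must first have settled to Grade 1 or lower.

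At stake is subject safety in the period right after a DLT. Sponsor and investigator can have the discussion that 5.9 asks for, comply with 5.9 fully, and still resume or continue preladenant while the DLT is unresolved. The condition that would prevent this was added to one section and not carried to the other.

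**Working it through.** No sample size, rate or error probability is involved, so the check is a comparison of texts.

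**Step 1: the two rules side by side**

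| | Section 5.2.2.1 | Section 5.9 |
|---|---|---|
| Default after a Cycle 1 DLT | Discontinue (*should*) | Discontinuation optional (*may*) |
| Clinical benefit needed to continue | Yes | Yes |
| Sponsor discussion needed | Yes | Yes |
| DLT resolved to Grade 1 or lower | Yes | Not mentioned |

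They disagree on the first and last rows. The pointer in 5.9 does not import the last row, because it is limited to replacement.

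**Step 2: which text to correct.** The Summary of Changes shows a deliberate addition to 5.2.2.1 and nothing for 5.9. The log is used here only to show intent.

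**Step 3: what other rules already require a hold**

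- *Table 7 (preladenant).* Grade 4 hematologic toxicity, Grade 3 lasting more than 5 days, febrile neutropenia, bleeding with Grade 3 thrombocytopenia, and most Grade 3-4 non-hematologic toxicity lead to a hold until baseline or Grade 1. Its notes require resolution to Grade 0-1 or baseline before restarting after a Grade 4 drug-related event. Two features make it looser than 5.2.2.1: return to baseline is accepted as an alternative, and Section 5.2.3.1 allows exceptions to the tables after sponsor consultation.
- *Arm 2, event attributed to the combination.* Section 7.2.4 makes this the general default. Section 5.2.3.1 then has both drugs held, and conflicting recommendations are settled by the more conservative one. Table 8 mostly requires resolution to Grade 0-1 or permanent discontinuation. It does so for Grade 2 AST, ALT or bilirubin, and its row for other Grade 3 toxicity has no laboratory carve-out and no duration threshold. Some endocrine rows use other criteria.

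**Step 4: what is left.** Mainly Arm 1, and Arm 2 events attributed to preladenant alone, where Table 7 does not mandate a hold. Two examples:

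1. *Grade 3 laboratory value.* Under DLT criterion 4 in Section 5.2.2 it is a DLT if "The abnormality persists for >72 hours", unless the exception for non-significant, treatable or reversible abnormalities applies. Table 7's Grade 3-4 non-hematologic row is limited by the words "not including laboratory, unless clinically significant medical intervention is required to treat the subject, or the abnormality leads to hospitalization", or unless the abnormality lasts more than 1 week. A value past 72 hours, not yet past 1 week, with no such intervention or admission, is a DLT without a mandated hold.
2. *Hy's Law DLT with Grade 2 values.* Criterion 5 uses multiples of the upper limit of normal: ALT or AST above 3 times, bilirubin above 2 times. If the values grade as 2, Table 7 leaves the hold to the investigator. This assumes that Grade 3 starts above those multiples, and the documents do not give the bilirubin cut-off. If Grade 3 bilirubin started at or below 2 times the limit, the event would fall under the Grade 3-4 row and this would no longer be a separate case.

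**Step 5: effect on the dose-finding.** Section 8.5.1 counts a subject who had a DLT within the 21 days whether or not treatment goes on. The inputs to Table 4 do not change.

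**The case against.** The strongest reply is that the two texts can be followed together. Section 5.9 only permits; a site that obeys 5.2.2.1 never breaches 5.9, and both routes go through the sponsor. That is right as logic, but it works in one direction only. A site that relies on 5.9 can breach 5.2.2.1, and neither section says which governs.

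The second reply is that other safeguards exist. Besides Tables 7 and 8, Section 7.1.3.1 requires laboratory results to be reviewed and found acceptable before each dose. Section 7.2.3.2 makes essentially the Hy's Law pattern an event of clinical interest, reportable within 24 hours, and refers sites to follow-up guidance in a binder that is not part of these documents. This reply largely stands and is why the point is modest. But the laboratory review, the 24-hour reporting and the sponsor discussion in 5.9 set no resolution grade in the text that can be read here.

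A reader might go further and infer that, outside 5.2.2.1, nothing stops re-dosing with an unresolved DLT. Tables 7 and 8 contradict that for most events, and the binder guidance cannot be ruled out as a further source. A reader might also infer that dosing continued within Cycle 1 must be at the dose that caused the DLT, because the note below Table 7 bars reductions in Cycle 1. Section 5.2.1.4 allows for adjustments in the DLT period after sponsor discussion, and Section 5.2.3.1 allows exceptions, so that does not follow either.

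**Conclusion.** The conflict is real and rests on the wording of two current sections alone. Section 5.9 omits a safety condition that was deliberately added to 5.2.2.1, and it weakens the default from *should* to *may*.

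Its practical reach is limited to DLTs for which neither Table 7 nor Table 8 forces a hold. The Grade 3 laboratory example assumes that the exception in criterion 4 does not apply. It also needs persistence beyond 72 hours to be documented, and Cycle 1 chemistry is scheduled only on Days 1, 8 and 15, so an unscheduled test may be needed. The Hy's Law example depends on the bilirubin cut-off noted above. The conflict between 5.2.2.1 and 5.9 depends on neither example.

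No number of affected subjects or doses can be given: the documents do not say how many subjects with a DLT would be benefiting, or how many would still be above Grade 1. It would be tempting to read this as a threat to the dose-finding, but the DLT is counted either way, so the escalation decisions and the RP2D are not affected. This is a point to consider, and worth acting on because the correction is so small.

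**What to change.** In Section 5.9, replace the paragraph on a subject who experiences a DLT in Cycle 1 with one sentence: *Continuation after a DLT follows Section 5.2.2.1.*

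Section 5.2.2.1, the DLT criteria, Tables 4, 7 and 8, and Section 8.6.2 stay as they are. The change needs no new data, visits or analyses. The only thing given up is a discretion that 5.2.2.1 already withholds.
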